## 7.10 Discontinuation of Treatment

The reasons for discontinuation or protocol treatment include:

- Evidence of disease progression during treatment at the discretion of the treating investigator
- Non-compliance with the study protocol, including, but not limited to not attending the majority of scheduled visits. The Protocol Chair will determine when non-compliance should lead to removal from study. Note: These patients will still be included in the overall evaluation of safety and response
- Unacceptable major toxicity. Note: These patients will still be included in the overall evaluation of safety and response

- Intercurrent illness or condition that would, in the judgment of the treating investigator, affect assessment of clinical status to a significant degree or require discontinuation of study treatment
- At subject's own request. Note: The reason for discontinuation from the study must be documented. These patients will be included in the overall evaluation of safety and response if any protocol therapy was administered prior to withdrawal
- Study is closed for any reason (e.g. new information shows that the patient's welfare would be at risk if she continued study treatment)
- General or specific changes in the participant's condition render the participant unacceptable for further treatment in the opinion of the treating investigator
- Patients that require a dose delay of > 28 days. If the delay is due to a cause unrelated to study participation, the patient will have the opportunity to continue study if beyond the first 8 weeks of treatment, if clinical benefit is seen, and if deemed eligible to do so by the Protocol Chair of the study
- If the patient requires dose reduction below dose level -1, the patient should be discontinued from the study unless deemed to have clinical benefit that would outweigh the risk. A discussion with the Protocol Chair should be carried out prior to final decision on discontinuation

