## 17.2 Sample Size and Statistical Analysis

### 17.2.1 Primary endpoint

Demographic and baseline patient characteristics will be summarized. Adverse events will be classified by type, incidence, severity, and causality. All adverse events will be summarized by patient, dose level, and disease. All patients who received at least 4 weeks of study treatment drugs (unless DLTs observed) will be included in the **safety** portion of the trial, and all patients who received at least 8 weeks of erdafitinib will be included in the **tolerability** portion of the trial.

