Since a phase II study is currently being planned, tolerability and experience with these combinations over at least 8-16 weeks is desirable. A period of 8 weeks was deemed acceptable for assessment of study drug tolerability. Hence, we are proposing a modified definition of an MTD, to ensure tolerability of study drugs for a more prolonged period of time in anticipation of future phase II trials. We plan to treat at least 20 patients as part of the expansion portion of the study. For tolerability assessment, patients in the escalation portion of the trial that are treated at the MTD will be included in the tolerability analysis.

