#### Justification for RP2D based on $\geq 15$ out of 20 Tolerant Patients

	0.3	True probability of tolerability at MTD						
		0.5	0.7	0.75	0.8	0.9	0.99	
Probability of observing $\geq 15/20$ tolerable patients	0.00004	0.02	0.42	0.62	0.80	0.99	1.00	

#### Two-sided 95% Wilson Confidence Intervals\* for the Probability of Treatment Tolerance based on $\geq 15$ Tolerant Patients out of 20

Observed # of tolerant patients	95% Wilson confidence interval	
	Lower bound	Upper bound
15	0.53	0.89
16	0.58	0.92
17	0.64	0.95
18	0.70	0.97
19	0.76	0.99
20	0.84	1.00

\* We chose to calculate and report the Wilson score confidence intervals because of their good coverage properties, especially when the true proportions are at extreme values such as

being equal to or close to 1

([http://en.wikipedia.org/wiki/Binomial\\_proportion\\_confidence\\_interval](http://en.wikipedia.org/wiki/Binomial_proportion_confidence_interval)).

The recommended dose for phase II trials will be defined as the highest dose (at or below the MTD) at which  $\geq 15$  patients treated at the MTD (including patients from the escalation portion treated at that same dose level) can tolerate treatment for a minimum of 8 weeks in a row without development of the previously cited toxicities. The dose that will be used in the phase II study will be the most tolerable (i.e. with the least amount of  $\geq$  Grade 2 toxicities), as tested in this study. Study drugs will be given at the specified doses above until disease progression or unacceptable toxicity. As long as the above parameters are fulfilled (i.e. at least 15 out 20 patients are able to safely tolerate the combination at a given dose level stipulated by the study for 8 weeks in a row) the dose of study drugs in the expansion portion of the study (i.e. the highest tolerable dose; not necessarily the MTD) will move forward in phase II studies.

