### 17.3 Reporting and Exclusions

All patients included in the study must be assessed for safety, tolerability, and response to treatment, even if there are major protocol treatment deviations or if they are ineligible. Each patient will be assigned one of the following categories: 1) complete response, 2) partial response, 3) stable disease, 4) progressive disease, 5) early death from malignant disease, 6) early death from toxicity, 7) early death because of other cause, or 9) unknown (not assessable, insufficient data). All of the patients who met the eligibility criteria (with the possible exception of those who received no study medication) should be included in the main analysis of the response rate. Patients in response categories 4-9 should be considered to have a treatment failure (disease progression). Thus, an incorrect treatment schedule or drug administration does not result in exclusion from the analysis of the response and clinical benefit rate.

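### The tolerability set in Section 17.2.1 is defined by reaching 8 weeks of erdafitinib, which is part of the outcome, and the 15-patient rule is justified only for 20 patients although the plan can pool more

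*Combined protocol and SAP*

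**What the plan says.** Section 17.2.1 defines two analysis sets in one sentence. The safety set needs at least 4 weeks of study treatment, with an exception for patients who have a DLT. For the second set, "all patients who received at least 8 weeks of erdafitinib will be included in the" tolerability portion of the trial; no exception is given.

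The outcome comes later in the same section, under the justification for the RP2D: patients count if they "can tolerate treatment for a minimum of 8 weeks in a row without development of the previously cited toxicities". The rule for carrying a dose into phase II appears in two forms. One is a count of at least 15 patients treated at the MTD, escalation patients at that level included. The other, with the same 8-week requirement, is that "at least 15 out 20 patients are able to safely tolerate the combination at a given dose level stipulated by the study". The printed pass probabilities and Wilson intervals are all for 20 patients.

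On numbers, 17.2.1 says "We plan to treat at least 20 patients as part of the expansion portion of the study", and that "patients in the escalation portion of the trial that are treated at the MTD will be included in the tolerability analysis". The dose table in Section 7.3 gives 3 to 6 patients per level.

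Two other places bear on who is counted. Section 17.3 says "All patients included in the study must be assessed for safety, tolerability, and response to treatment". Section 7.10 lists as a reason for stopping treatment "Unacceptable major toxicity. Note: These patients will still be included in the overall evaluation of safety and response"; it does not mention tolerability.

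**The concern.** There are two problems, and they act on different quantities.

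The first is the set. If entry requires 8 weeks of erdafitinib, patients whose erdafitinib ends for toxicity before then cannot be counted as failures, because they are not in the set. The assessment is meant to add experience beyond the 4-week DLT window, and toxicity stops in weeks 5 to 8 are among those that drop out. The missing exception does not look like shorthand, since the safety set in the same sentence has one. Two analysts, one following 17.2.1 and one following 17.3, would report different tolerability rates from the same data.

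The second is the denominator of the dose rule. The threshold of 15 has known properties only when 20 patients are counted. If more are pooled and the count stays at 15, the rule is easier to pass than the printed table says. This result selects the dose for the planned phase II trial.

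**Working it through.** **Inputs.** Threshold 15 and denominator 20 (17.2.1, justification for the RP2D); at least 20 expansion patients plus the escalation patients at the MTD (17.2.1); 3 to 6 patients per dose level (Section 7.3). Assumption: exactly 20 expansion patients. The pooled number is then N = 20 + 3 = 23 or N = 20 + 6 = 26.

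**Step 1: reproduce the printed table.** P(pass) = P(X ≥ 15), with X binomial (20, p). For p = 0.5, 0.7, 0.75, 0.8 and 0.9 this gives 0.021, 0.416, 0.617, 0.804 and 0.989; printed are 0.02, 0.42, 0.62, 0.80 and 0.99. The Wilson interval for 15/20 is 0.531 to 0.888; printed is 0.53 to 0.89. The plan's arithmetic for 20 patients is correct.

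**Step 2: effect of the 8-week entry condition on the reported rate.** Let p be the true tolerability among all treated at the MTD and q the proportion who stop erdafitinib for toxicity before week 8. The rate inside the set is p/(1 − q). The documents give no q, so this is illustration only. With 20 treated, 4 early toxicity stops and 12 tolerant patients:

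| Denominator | Rate | 95% Wilson interval |
|---|---|---|
| All treated | 12/20 = 60% | 0.39 to 0.78 |
| At least 8 weeks of erdafitinib | 12/16 = 75% | 0.51 to 0.90 |

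The number of tolerant patients is 12 either way.

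**Step 3: when the entry condition also changes the decision.** If the 20 in the rule means 20 patients who reached 8 weeks, the pass probability is P(X ≥ 15) with X binomial (20, p/(1 − q)). For p = 0.6 and assumed q = 0.1, 0.2 and 0.3, p/(1 − q) is 0.667, 0.75 and 0.857, and the pass probability is 0.30, 0.62 and 0.94, against 0.13 at q = 0.

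**Step 4: the count left at 15 with more patients.** P(X ≥ 15), with X binomial (N, p):

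| N | True 50% | True 70% | Lowest passing rate | 95% Wilson interval |
|---|---|---|---|---|
| 20 (printed case) | 0.02 | 0.42 | 15/20 = 75% | 0.53 to 0.89 |
| 23 | 0.11 | 0.77 | 15/23 = 65% | 0.45 to 0.81 |
| 26 | 0.28 | 0.94 | 15/26 = 58% | 0.39 to 0.74 |

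**Step 5: thresholds restated for the larger N.**

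| Rule | True 70% | True 80% |
|---|---|---|
| 15/20 (printed) | 0.42 | 0.80 |
| 17/23 | 0.44 | 0.84 |
| 19/26 | 0.46 | 0.87 |
| 20/26 | 0.30 | 0.75 |

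For N = 26, 19 is nearer the printed value at 70% and 20 is slightly nearer at 80%.

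**The case against.** **The set definition may not bind.** The sentence in 17.2.1 says who will be included; that nobody else is included is an inference, and 17.3 asks for all patients to be assessed. This stands as far as it goes, but the plan does not say which section governs. Section 7.10 does not settle it, because its note covers safety and response only.

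**Receiving 8 weeks is not the same as tolerating 8 weeks.** This also stands. The cited toxicities lead to dose reduction, so a patient who has one and continues at a lower dose to week 8 stays in the set and counts as a failure. Only failures whose erdafitinib ends before week 8 are lost.

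**The rest of 17.2.1 need not contradict the set.** A reader might infer that its later paragraphs on patients treated at the MTD conflict with the 8-week condition. They select by dose level and the condition selects by exposure, so both filters can apply together. The clear conflict is with 17.3.

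**The denominator is stated as 20.** The headings, the probability row and the closing form of the rule all use 20. That is fair, so the gap is narrower than an absent denominator. But the number 20 in the sample-size sentence is a minimum for the expansion alone, escalation patients are added to it, and nothing says which 20 count.

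**Larger N.** A reader might extend the calculation to nine escalation patients at the MTD (N = 29), since Table 17.2.1 allows staying at a dose after 1 or 2 DLTs in 6 patients. That exceeds the 3 to 6 per level in Section 7.3, so it is not used here. The two places should be reconciled.

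**Conclusion.** The concern holds in two limited parts.

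First, as written, the tolerability set leaves out patients who stop erdafitinib for toxicity before week 8, and the reported proportion and interval are then too high. The size depends on an early-stop rate that the documents do not give; 75% instead of 60% is an example, not an estimate. A reader might infer that this exclusion by itself lets a poorly tolerated dose through. Under the bare count of 15 it does not: with the number treated fixed, the excluded patients could never have been among the 15. It would affect the decision only if the 20 means 20 patients who reached 8 weeks, which the plan neither says nor rules out. The cycle 1 DLT assessment and the MTD are unaffected.

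Second, the 15-patient rule has no stated justification beyond 20 patients. With exactly 20 expansion patients plus 3 or 6 at the MTD and the count kept at 15, a true 70% passes with probability 0.77 or 0.94 instead of 0.42, and a true 50% with 0.11 or 0.28 instead of 0.02. This part bears directly on the phase II dose choice. It assumes that all pooled patients are counted against 15; if 20 specified patients are counted, the printed table applies.

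**What to change.** In 17.2.1, define the tolerability set as all patients, escalation and expansion, whose assigned starting dose level is the MTD and who receive at least one dose, except those replaced under Section 7.11 for reasons clearly not related to study treatment.

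State that a patient is not tolerant if erdafitinib is stopped before 8 weeks because of toxicity, or if one of the cited toxicities develops within 8 weeks, even when treatment continues at a reduced dose. The outcome definition already implies the second part.

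Fix the denominator in advance, in one of two ways:

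- the first 20 such patients in order of first dose, keeping 15 of 20 and the printed tables; or
- all N such patients, with the threshold and both tables restated for that N, for example 17/23, or a choice between 19/26 and 20/26 on the figures above.

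Then align the set definition, the RP2D rule and Section 17.3, and reconcile the 3 to 6 per level in Section 7.3 with Table 17.2.1.

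The cost is wording, plus recalculated tables under the second option; no new visits or data are needed. The reported rate may be less favourable, and the first-20 option leaves later patients at the MTD out of the decision count.

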## 7. TREATMENT PLAN

### 7.1 Overview

This is an open-label, multi-institution, phase Ib (3+3 dose escalation design) that evaluates the safety profile (assessment of DLTs and MTD of the combination), tolerability and anti-tumor activity (progression-free survival [PFS] and lack of disease progression for  $\geq$  6 months [clinical benefit rate; CBR]) of fulvestrant, palbociclib and erdafitinib in patients with metastatic ER+/HER2-/FGFR-amplified breast cancer.

When feasible, a baseline biopsy of a metastatic site will be obtained for NGS and/or *FGFR* FISH prior to therapy initiation. Plasma will also be obtained at baseline, 4 weeks after treatment initiation and at disease progression for measurement of cfDNA. Treatment will be given until disease progression or unacceptable toxicity. To assess for anti-tumor effects, we will estimate the overall tumor burden at baseline to which subsequent measurements (performed every 8 weeks using the Solid Tumor Response Criteria [RECIST] v1.1) will be compared. Pharmacokinetic and pharmacodynamic studies will be obtained throughout the study.

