## 7.5 Definition of Maximum Tolerated Dose (MTD)

The MTD will be defined as the highest dose at which 20% of the patients experienced a DLT. The first cohort of patients (3 patients) will be started at dose level 1, and each patient will be observed for 4 weeks on the specified dose. No new cohort of patients will be treated until the previous cohort has been fully evaluated for toxicity and a dose escalation decision has been made. Routine updates regarding patient and study status will be conducted.

Once the MTD is reached, the safety data will be analyzed and the expansion component of the study will be completed to assess tolerability and efficacy. Patients in the phase II portion of the study will initiate study treatment at the MTD defined in the escalation component of the trial. Note that dose reduction within patients (individually) is allowed after the 4 week DLT observation period in the escalation and in the expansion components of the study (see Dose Modification guidelines, Section 8). Intrapatient dose escalation will not be allowed. Dose reduction will be required for a given patient in case of:

- Grade 3 or 4 toxicities
- Grade  $\geq 2$  hyperphosphatemia lasting more than 21 days despite medical treatment, or
- Grade  $\geq 2$  ocular toxicity lasting more than 28 days despite medical treatment, or
- Grade  $\geq 2$  elevation of creatinine, bilirubin, AST, or ALT lasting more than 14 days despite medical treatment, or
- Grade  $\geq 2$  skin or nail toxicity for more than 28 days in a row despite optimal medical treatment, or

- Grade  $\geq$  2 GI toxicity lasting more than 14 days despite medical treatment.

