### **7.11 Replacement of Patients Who Discontinue Early**

In general, the study intends that patients would be treated until disease progression or intolerable toxicity. During the phase Ib dose escalation period and phase II portion of the study, if a patient discontinues study treatment for reasons clearly not related to study treatment, after completing fewer than one planned cycle of study, and/or receiving <75% of the total intended dose of study drugs over the first cycle of treatment, then that patient will be considered not evaluable and may be replaced with a new patient.

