In the phase Ib escalation component of the trial, the MTD will be defined using the recently developed adaptive design known as the modified toxicity probability interval (mTPI) method. The mTPI design uses a Bayesian framework with a beta/binomial hierarchical model to compute the posterior probabilities of three intervals that reflect the relative distance between the toxicity rate of each dose level to the target toxicity probability. That is, the mTPI design replaces the 3 + 3 rules with a model-based inference on the toxicity probability intervals and has been shown to be safer and more reliable than the 3+3 design. The first cohort of patients (3 patients) in each arm will be started at dose level 1, and each patient will be observed for 4 weeks on the specified dose. The maximum tolerated dose (MTD) will be defined as the highest dose at which 20% of the patients experienced a DLT. The levels of uncertainty around the true target toxicity  $p_T$  are (0.05, 0.05), which define the proper dosing interval as  $(p_T - 0.05, p_T + 0.05)$ . Each cohort has 3 patients. In **Table 17.2.1**, the columns are the numbers of patients treated so far at the current dose level, and the rows are the corresponding numbers of patients experiencing toxicity. The entries of the table are dose-finding decisions—E, S, and D—representing escalating the dose, staying at the same dose, and de-escalating the dose, respectively. In addition, decision U means that the current dose level is unacceptable because of high toxicity and should be excluded from the trial. For example, when one of three patients experiences toxicity, the decision is to stay at the current dose level. This means that the next cohort of 3 patients will be treated at the same dose level currently being used. If zero of three patients experiences toxicity, the decision is to escalate. This means that the next cohort of 3 patients will be treated at the next-higher dose level. If three of three patients experiences toxicity, the decision is DU—to de-escalate to the next-lower dose level and exclude the current dose from the trial which is considered unacceptably toxic.

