**Table 17.2.1**

		Number of Patients																	
		1	2	3	4	5	6	7	8	9	10	11	12	13	14	15	16	17	18
Number of Patients with DLTs	0	E	E	E	E	E	E	E	E	E	E	E	E	E	E	E	E	E	
	1	D	D	S	S	S	S	S	E	E	E	E	E	E	E	E	E	E	
	2	D	DU	D	S	S	S	S	S	S	S	S	S	S	S	S	E	E	
	3	DU	DU	DU	DU	D	S	S	S	S	S	S	S	S	S	S	S	S	
	4	DU	DU	DU	DU	DU	DU	D	S	S	S	S	S	S	S	S	S	S	
	5	DU	DU	DU	DU	DU	DU	DU	DU	DU	S	S	S	S	S	S	S	S	
	6	DU	DU	DU	DU	DU	DU	DU	DU	DU	DU	DU	DU	DU	DU	S	S	S	
	7	DU	DU	DU	DU	DU	DU	DU	DU	DU	DU	DU	DU	DU	DU	DU	DU	DU	
	8	DU	DU	DU	DU	DU	DU	DU	DU	DU	DU	DU	DU	DU	DU	DU	DU	DU	
	9	DU	DU	DU	DU	DU	DU	DU	DU	DU	DU	DU	DU	DU	DU	DU	DU	DU	
	10	DU	DU	DU	DU	DU	DU	DU	DU	DU	DU	DU	DU	DU	DU	DU	DU	DU	
	11	DU	DU	DU	DU	DU	DU	DU	DU	DU	DU	DU	DU	DU	DU	DU	DU	DU	
	12	DU	DU	DU	DU	DU	DU	DU	DU	DU	DU	DU	DU	DU	DU	DU	DU	DU	
	13	DU	DU	DU	DU	DU	DU	DU	DU	DU	DU	DU	DU	DU	DU	DU	DU	DU	
	14	DU	DU	DU	DU	DU	DU	DU	DU	DU	DU	DU	DU	DU	DU	DU	DU	DU	
	15	DU	DU	DU	DU	DU	DU	DU	DU	DU	DU	DU	DU	DU	DU	DU	DU	DU	

16												DU	DU	DU
17												DU	DU	
18														DU

**E:** Escalate to the next higher dose; **S:** Stay at the same dose; **D:** De-escalate to the previous lower dose; **DU:** De-escalate to the previous lower dose and the current dose will never be used again in the trial;

No new cohort of patients will be treated until the previous cohort has been fully evaluated for toxicity. All patients treated to determine the MTD will be part of the escalation portion of the trial.

Once the MTD is reached, the safety data will be analyzed and the expansion component of the study will be completed to assess tolerability and efficacy. Patients in the expansion component of the study will initiate study treatment at the respective MTD. Note that dose reduction within individual patients is allowed in the expansion component of the study. Dose reduction will be required for a given patient in case of grade 3 or 4 toxicities, or if grade 2 creatinine, bilirubin, AST, ALT, hyperphosphatemia or grade 2 GI toxicity lasting more than 2 weeks.

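### The MTD sentence does not work as a selection rule for mTPI data: its workable readings can name different doses from the same data, and sections 7.1 and 7.3 do not agree with 17.2.1

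*Combined protocol and SAP*

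**What the plan says.** Determination of the MTD is listed as a primary endpoint in the Synopsis and in section 2. Section 7.5 states: "The MTD will be defined as the highest dose at which 20% of the patients experienced a DLT". Section 17.2.1 repeats it in the paragraph that introduces the mTPI design: "The maximum tolerated dose (MTD) will be defined as the highest dose at which 20% of the patients experienced a DLT".

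The same paragraph gives the mTPI set-up. Cohorts are of 3 and the start is dose level 1 (5 mg). "The levels of uncertainty around the true target toxicity" are 0.05 on each side. Taking 20% as the target, which the context supports, the proper dosing interval is 0.15 to 0.25. Table 17.2.1 gives the moves E, S, D and DU. On E the text says: "This means that the next cohort of 3 patients will be treated at the next-higher dose level". The highest level in 7.3 is 8 mg.

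On the end of escalation, the text after the table says: "Once the MTD is reached, the safety data will be analyzed and the expansion component of the study will be completed". Expansion patients start at the MTD, at least 20 of them are planned, and the phase II dose must lie at or below the MTD.

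On the type of design, 7.1 reads: "This is an open-label, multi-institution, phase Ib (3+3 dose escalation design) that evaluates the safety profile". Section 17.2.1 reads: "the mTPI design replaces the 3 + 3 rules with a model-based inference on the toxicity probability intervals". The dose table in 7.3 lists 3-6 patients at every level.

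**The concern.** mTPI separates two tasks: moving between doses during escalation, and choosing the MTD from the final data. Table 17.2.1 settles the first. For the second the protocol offers one sentence, and it contains no inequality, no closest-to criterion and no minimum number of patients. An observed rate of exactly 20% is rarely attainable in cohorts of 3, so whoever declares the MTD must substitute another reading, and the text does not say which.

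The choice has consequences. The MTD is the starting dose for at least 20 expansion patients and the ceiling for the phase II dose. If 6 mg is declared where another fair reading gives 8 mg, the later tolerability rule cannot bring 8 mg back. If 8 mg is declared, the expansion cohort starts there.

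The sections also pull apart at 2/6. The table says Stay, whereas a conventional 3+3 reading, prompted by 7.1, would rule the dose out.

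**Working it through.** **1. Reproduce the plan's decisions.** Inputs from 17.2.1: target pT = 0.20, half-widths 0.05, cohorts of 3. Assumed because not stated: a Beta(1,1) prior, and DU when P(p > 0.20) > 0.95. With x DLTs in n patients the posterior is Beta(1+x, 1+n-x). The decision is the interval with the largest posterior probability per unit length, among (0, 0.15), (0.15, 0.25) and (0.25, 1).

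| Data | E | S | D | P(p > 0.20) | Decision |
|---|---|---|---|---|---|
| 0/3 | 3.19 | 2.06 | 0.42 | 0.41 | E |
| 1/3 | 0.73 | 1.52 | 0.98 | 0.82 | S |
| 2/6 | 0.49 | 1.70 | 1.01 | 0.85 | S |
| 2/9 | 1.20 | 2.95 | 0.70 | 0.68 | S |

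These match Table 17.2.1. The three examples in the text (0/3 = E, 1/3 = S, 3/3 = DU) are reproduced as well.

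**2. Literal reading.** x/n = 0.20 for n up to 18 requires 1/5, 2/10 or 3/15. Only 15 is a multiple of 3. The other two need incomplete cohorts, which can arise because under 7.11, for certain early discontinuations, "that patient will be considered not evaluable and may be replaced with a new patient": replacement is optional. The stated totals imply at most 35 - 20 = 15 escalation patients, so 3/15 could occur only if all 15 were treated at the 5 mg starting level.

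**3. A path on which every move follows the table.** 5 mg 0/3 (E); 6 mg 0/3 (E); 8 mg 1/3 (S), 2/6 (S), 2/9 (S).

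| Final data at 8 mg | Escalation patients | Exactly 20% | At most 20% | Closest to 20% |
|---|---|---|---|---|
| 2/6 = 33.3% | 12 | none | 6 mg | 8 mg |
| 2/9 = 22.2% | 15 | none | 6 mg | 8 mg |

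For closest to 20%, the isotonic estimates at 5, 6 and 8 mg are 0, 0, 0.333 or 0, 0, 0.222. The distances from 0.20 at 8 mg are 0.133 and 0.022, against 0.20 at 6 mg.

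**4. At most 20% against the table.** The recomputed Stay cells at n = 3, 6, 9, 12 and 15 are 1/3, 1/6, 2/6, 2/9, 3/9, 2/12, 3/12, 4/12, 2/15, 3/15, 4/15 and 5/15. Eight of the 12 exceed 20%, so that reading rejects doses at which the table says to stay.

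**5. How often the readings differ.** Exact enumeration, start at 5 mg, E at 8 mg taken as S, D or DU at 4 mg ending with no MTD, at most 15 patients. The DLT rates are assumptions. The first two result columns count trials in which both readings name a dose and the doses differ.

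| Assumed DLT rate at 4/5/6/8 mg | Run to 15 | Stop at 6 per dose | 6 v 8 mg, run to 15 | 6 v 8 mg, stop at 6 |
|---|---|---|---|---|
| .02/.05/.08/.12 | .18 | .11 | .16 | .07 |
| .05/.08/.12/.20 | .27 | .17 | .21 | .10 |
| .10/.15/.20/.30 | .24 | .18 | .13 | .08 |
| .10/.20/.30/.40 | .18 | .16 | .06 | .04 |
| .20/.30/.40/.50 | .08 | .09 | .01 | .01 |
| .05/.10/.20/.35 | .28 | .22 | .14 | .10 |

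Run to 15, no dose shows exactly 20% in 92-99% of trials. At most 20% names no dose where closest to does in a further 0-34%. The upper end comes from the curve with a 20% rate even at 4 mg; the other five give 0-16%.

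**6. Patients per level.** The table says Stay at 1/6 and at 2/6, so the next cohort takes that level to 9. Section 7.3 gives 3-6. The two agree only if 6 is a per-level cap, which 17.2.1 does not state.

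**The case against.** **The stated interval may supply the reading.** The definition is followed directly by the interval 0.15 to 0.25, and 2/9 = 22.2% lies inside it. Replacing at most 20% by at most 25% cuts the run-to-15 disagreement with closest to from 8-28% to 3-11%. This has force, but the text does not present the interval as a selection rule. It also does not help at 2/6, or anywhere under a stop at 6, since no rate with 3 or 6 patients lies between 20% and 25%.

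**The cited mTPI paper may specify final selection.** That cannot be checked from the documents. The rule is not written into the protocol, and the explicit 20% sentence would compete with it.

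**The harm is bounded.** This stands. The phase II dose also needs at least 15 of 20 patients tolerating treatment, expansion patients may be dose-reduced, and 8 mg is the single-agent starting dose given in section 9.1. It lowers the severity but does not supply a selection rule.

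**Stronger readings that the documents do not support.**
- A reader might infer that 3-6 in 7.3 is leftover 3+3 text. It may instead be an intended cap at 6, which would agree with the stated minimum (26 - 20 = 6). The documents show a conflict, not its origin.
- A reader might infer that escalation itself is undefined. It is not: the table gives the moves, and only E at 8 mg lacks an action.
- A reader might take the table's rows as left-justified and obtain 14-37% disagreement. That alignment puts entries in impossible cells, such as 5 DLTs in 1 patient, so it reflects a broken table rather than the plan.
- A reader might conclude that the sponsor will choose the reading after seeing the DLTs. The text leaves this open; it does not show it.

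**Conclusion.** Wrong as written; should be fixed. The literal MTD sentence cannot select a dose from almost any data set the design can produce, and its plausible substitutes can give 6 mg or 8 mg from the same patients. The worked path needs no assumed DLT rates.

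The frequencies do rest on assumptions: the six curves, a Beta(1,1) prior, the 15-patient limit implied by the totals, and an isotonic closest-to rule that the protocol does not state. On that basis the doses differ in 8-28% of trials run to 15, or 9-22% with a stop at 6. The 6 versus 8 mg split is the narrower 1-21%, or 1-10%.

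The 3+3 label in 7.1 plainly contradicts 17.2.1. The 3-6 in 7.3 is a conflict unless it is a cap. Because the tolerability rule and dose reductions stand between the MTD and the phase II dose, this falls short of a fault that would by itself put a wrong dose into phase II.

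**What to change.** - **7.1:** replace the 3+3 description with: mTPI, see 17.2.1.
- **7.5 and 17.2.1:** state pT = 0.20 and replace the MTD sentence with:

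> The MTD is the tried dose, not marked DU, whose isotonic-regression DLT estimate is closest to 0.20; ties below 0.20 go to the higher dose, all other ties to the lower. E at 8 mg, or when the next dose is marked DU, is treated as S; D or DU at dose level -1 ends escalation with no MTD.

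- **17.2.1:** write down the escalation limit the totals already imply, at most 15 patients (35 - 20), and say whether replaced patients count towards it.
- **7.3:** say whether 3-6 is a per-level cap, so that it agrees with 17.2.1.

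Under this rule the worked path gives 8 mg at either 2/6 or 2/9. Data with no DLTs at 5, 6 and 8 mg also give 8 mg, through the tie rule.

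The cost is a wording amendment in four sections, with no change to the stated totals provided replaced patients count within them. The per-dose stop (6, 9 or none) is the sponsor's trade-off and is not part of the required fix. Under the same six curves and the closest-to rule, a stop at 6 saves 4.4 to 6.2 escalation patients on average against always using 15. It changes the chance of choosing the dose with true rate nearest 0.20 by -0.12 to +0.04, lowering it on five of the six curves.
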